178 For certain endpoints, supplementation of cadaveric controls above those identified in the
179 retrospective cohort component of the study may be necessary. Augmentation with
180 contemporaneous cadaveric controls would most likely occur for the first one to two
181 years of a program's experience. If additional patients are required, they will be
182 identified using SRTR data, frequency matching to the characteristics of recipients
183 undergoing LDLT. Potentially, a few LDLT patients could be included in this group but
184 excluded from the primary objective analysis. This situation would arise if a donor
185 evaluation occurred in 1997, resulting in LDLT in early 1998, although this comprises a
186 very small number of patients. We anticipate supplementation with no more than 100 to
187 200 transplant recipients.

188

189 The final cohort will include the LDLT donors (approximately 300).

190 **4.2. Comparison of mortality between LDLT and non-LDLT recipients**

191 **4.2.1. Study Methods**

192 The primary aim will use the cohort of subjects evaluated for LDLT. Survival from time
193 of donor evaluation will be compared among those receiving and not receiving LDLT. In
194 addition, we will compare both survival and rejection episodes for LDLT vs. cadaveric
195 recipients from time of transplant.

196

197 Primary endpoint: Time of death or last known alive.

198 Secondary endpoint: Time from transplant to rejection episode, or last known time
199 without rejection, incidence, number and severity of rejection and incidence of steroid-
200 resistant rejection during the 1st post-transplant year.

201 **4.2.2. Participant Selection**

202 The cohort will include all of the following:

203 Potential recipient listed for liver transplantation

- 204 • age \geq 18
- 205 • single organ

206

207 Potential donor evaluated with history and physical examination occurring between
208 1/1/1998 and the start date of the A2ALL-Cohort-01 Study enrollment. This date will be
209 different for each clinical site and will be determined once site initiation is completed and
210 the site is ready to begin enrollment of prospective subjects.

211 **4.2.3. Data Elements**

212 Two limitations of chart reviews must be kept in mind: Information may be missing, and
213 information may be inaccurate. Because these problems can occur systematically, results
214 can be biased. A2ALL will be circumspect about collecting information that is limited in

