302 evaluated for LDLT, and were alive and eligible for transplant at the same time following
303 donor evaluation as the LDLT patient was when they received their transplant. This
304 analysis will involve a different set of controls for each patient, with many control
305 patients re-used in several control sets. A modified Cox regression will be performed,
306 with statistical adjustment for the re-use of controls. In both Cox analyses, variables will
307 be checked to ensure that the proportional hazards assumption is met. If non-proportional
308 hazards are detected, particularly for the LDLT effect, they will be modeled using time-
309 dependent covariates. Interactions between covariates and the LDLT effect will be
310 tested.

311
312 Survival from date of surgery for LDLT versus cadaveric transplant will also be
313 compared using Cox regression, adjusted for prognostic variables. The distributions of
314 time from transplant to rejection episode between LDLT and cadaveric transplant will be
315 similarly compared.

316
317 We will also analyze the incidence, timing, and diagnosis (biopsy-proven or not) of
318 clinically evident liver transplant rejection requiring treatment. Analyses of rejection will
319 include subsets restricted to biopsy-proven and steroid-resistant rejection episodes.

320 **4.3. Study of Hepatitis C Virus Infection**

321 **4.3.1. Study Methods**

322
323 LDLT recipients transplanted for HCV will be compared to an approximately equal
324 number of contemporaneous cadaveric controls selected from SRTR based on a diagnosis
325 of HCV. If SRTR data are not complete for HCV identification, identification of HCV
326 patients at the facility level may be required.

327 (Note: Post-transplant biopsies will be re-read by the local pathologist for grade, stage,
328 and other characteristics of recurrent HCV. The biopsy performed closest to the one-year
329 anniversary of transplant (+/- 3 months) will be employed for histologic scoring)

330

331 Primary end-point

332

333 a) Severity of disease based upon Knodell (necroinflammatory) and Ishak
334 (fibrosis) scores on liver biopsy at 1 year (\pm 3 months) post-transplant in LDLT
335 and cadaveric transplant.

336

337 Secondary end-points

338

339 a) Rate of fibrosis progression (comparison of 0, 1 year and most recent biopsy
340 [the latter must be a minimum of 12 months after the 1-year biopsy] in LDLT
341 and cadaveric transplants)

342 b) Proportion with cholestatic hepatitis

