469 cadaveric transplant recipients, no supplemental contemporaneous cadaveric controls will
470 be used.

471 **4.4.3. Data Elements**

472 Maximum size and number by radiology pre-transplant and at transplant (explant)
473 Whether Milan criteria were met
474 Whether HCC was an incidental finding.
475 Date of diagnosis of disease recurrence post-transplant.
476 Number and type of HCC ablation procedures.

477 **4.4.4. Sample Size and Power Calculations**

478 We anticipate approximately 75 hepatocellular carcinomas among the ~ 300 LDLT cases,
479 and approximately 125 among the ~ 500 non-LDLT cases who were also evaluated for
480 LDLT. With 75 LDLT cases and 125 non-LDLT cases, we will have 90% power to
481 detect a difference in recurrence (or presence) of HCC of 10% versus 30%. Since
482 reduction of HCC in the non-LDLT group will be due to subsequent cadaveric
483 transplantation, this statistical test will compare the strategy of LDLT versus waiting for a
484 cadaveric transplant.

485 **4.4.5. Statistical Analysis**

486 Initial analysis of HCC will be primarily descriptive. The characteristics of HCC patients
487 described will include TNM explant pathologic stage, use of ablation pretransplant, and
488 pre transplant ablation method (i.e. chemoembolization, RFA, etc.). The proportion
489 recurring within one year will be presented, with 95% CI. Predictors of one-year
490 recurrence will be explored using logistic regression for patients with at least one year of
491 follow-up. The difference between recurrence (or presence) proportions for LDLT versus
492 non-LDLT patients will also be estimated using a 95% confidence interval. A comparison
493 of survival between these two groups will be performed using Cox regression, adjusted
494 for various prognostic covariates. A comparison of survival between LDLT and
495 cadaveric transplant recipients will also be performed.

496 **4.5. SRTR Data Validation Study**

497 *(This section does not apply to subjects who have the first living donor evaluated after*
498 *2/28/03)*

499 **4.5.1. Study Methods**

500 We will investigate records for all patients with LDLT, and a subset of patients not
501 receiving LDLT. These patients will be selected as needed to develop comparison
502 cohorts for the other Retrospective research aims. All patients to be studied as part of
503 any Retrospective cohort will be included in this validation study.

504

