505 For each included patient, the A2ALL study coordinator will be asked to provide the
506 data, based on chart review, for a selected subset of SRTR data items. The coordinator
507 will be asked NOT to refer to copies of SRTR forms, but to provide the data based on
508 chart review (or personal knowledge) alone. These data will be entered in a web-based
509 data entry module. The module will have access to the original SRTR data, and will
510 check the new data against the original SRTR data and provide immediate feedback if a
511 discrepancy is found. The data coordinator will then resolve the difference, and either
512 confirm the new value or enter a corrected value. The original SRTR record, as well as
513 the final online entry, will be recorded in a special validation database.

514
515 The current SRTR data may be incomplete, and we have documented serious omissions
516 in the reporting of HCC data. However, because the SRTR data were submitted closer to
517 the time of listing and transplant, they may benefit from information available at those
518 times that was not documented in the patient charts. Thus, if a discrepancy is found
519 between the old SRTR data and the newly entered data, the coordinator will be given the
520 opportunity to decide which is correct.

521
522 Potential for bias may arise if the A2ALL coordinator is the same person who enters the
523 SRTR/OPTN data, or is a co-worker of that person. In that case, the A2ALL coordinator
524 may be more likely to simply validate the SRTR data, rather than checking to make sure
525 it is correct. We will attempt to minimize this bias by addressing the problem in the
526 coordinator training session. Coordinators will be instructed in the importance of
527 obtaining the data from chart review.

528 **4.5.2. Participant Selection**

529 All patients waitlisted for liver transplantation and considered for living donor
530 transplantation between 1/1/1998 and 2/28/2003 at any of the nine A2ALL centers. If
531 supplemental cadaveric transplant cases are used for any other specific aims, their data
532 may also be included in the validation study.

533 **4.5.3. Data Elements**

534 Validation of SRTR data elements will incorporate information from patients included in
535 all of the above studies.

536 **4.5.4. Sample Size and Power Calculations**

537 For an estimated proportion correct near 0.95 (95% correct), sample size of 300 will yield

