538 a 95% confidence interval (CI) for the true proportion will have a CI width of
539 approximately +/- 0.025. For estimated proportions near 0.50 (50% correct), a 95% CI
540 for the true proportion will have CI width of approximately +/- 0.057.

541 **4.5.5. Statistical Analysis**

542 The purpose of the data analysis is to document the correctness of the SRTR database.
543 For each data element we will calculate: (1) the percent missing in the original SRTR
544 data that were completed in the new data, (2) the percent of values that were not missing
545 in the original data but were changed (corrected) in the new data, and (3) the percent of
546 values that were correct in the original data. These percents should total 100%, unless an
547 original SRTR data value was deemed to be incorrect and replaced with a missing value.
548

549 An additional analysis will investigate whether data quality changed after introduction of
550 the electronic OPTN data submission system (UNet).
551

552 This validation study will tell us which of the SRTR data elements are reliable, and which
553 are not. For each data element, we will assume that the A2ALL centers are
554 representative of the other SRTR centers. Any data elements shown to be less than 95%
555 correct in the A2ALL centers should be analyzed with caution in the full SRTR database.
556

557 We will also investigate center variability, to determine if error rates are center-specific
558 or if they are similar across centers. This information will allow us to confidently use the
559 full SRTR database for selected retrospective analyses.

560 **4.6. Retrospective Post-surgical Complications Study**

561 **4.6.1. Study Methods**

562 The major objective of this portion of the study is to define the incidence of donor
563 morbidity in right lobe living donors in a retrospective cohort of patients and to compare
564 recipient morbidity after LDLT or cadaveric transplant.
565

566 The charts of all right lobe donors will be retrospectively reviewed using a defined
567 worksheet. The records of all patients who underwent a general anesthetic with the intent
568 to proceed with living donation will be included. This will allow us to capture patients
569 whose donation was aborted for various reasons. The hospital records, as well as any
570 outpatient ambulatory medical records, will be included in the review. Visits to outside

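### The SRTR validation may pool supplemental controls picked on SRTR fields, understating percent missing for those fields (chiefly HCV diagnosis); the effect is small and cheap to remove.

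*Protocol*

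**What the plan says.** **Who is validated.** Protocol 4.5.1 says that all patients studied in "any Retrospective cohort will be included in this validation study". Section 4.5.3 adds that the validation draws on patients from all the preceding studies, which include the HCV study. Section 4.5.2 defines the population differently. It starts from "All patients waitlisted for liver transplantation and considered for living donor" transplantation between 1/1/1998 and 2/28/2003, and then says that if "supplemental cadaveric transplant cases are used for any other specific aims, their data" "may also be included in the validation study".

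**How supplements are found.** Under 4.1, additional cadaveric recipients are "identified using SRTR data, frequency matching to the characteristics of recipients" of LDLT, with no list of those characteristics. Section 4.3.1 plans an approximately equal "number of contemporaneous cadaveric controls selected from SRTR based on a diagnosis" of HCV. Section 4.3.2 draws first on cadaveric controls already in the retrospective study and turns to SRTR only if they are too few. Section 4.6.2 matches on center and on transplant date within six months. Section 4.4.2 rules out supplements for the HCC comparison. Section 4.1 expects no more than 100 to 200 supplements overall.

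**How results are used.** For each data element, 4.5.5 reports the percent missing in SRTR but completed on review, the percent changed, and the percent correct. The three should total 100%. Elements less than 95% correct are to be analyzed with caution in the full registry.

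**The concern.** Part of the validation sample may be chosen on the content that the study is meant to check. Someone picked because SRTR records HCV cannot have a blank HCV diagnosis in SRTR, whatever the true omission rate. Such patients add to the denominator of percent missing and never to the numerator. The resulting bias in percent missing runs in one direction, does not shrink as the sample grows, and is not reflected in the confidence interval.

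The aim in 3.5.1 is to estimate completeness and correctness, and 3.5.2 uses the answer to decide which SRTR elements can serve the prospective cohort. The fields exposed to this bias are those on which SRTR-based selection depends. The sections also disagree on whether these patients are in the sample at all.

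**Working it through.** **1. The plan's own precision.** Section 4.5.4 gives half-widths of 0.025 and 0.057 for n = 300. With 1.96 × √(p(1 − p)/300), p = 0.95 gives 0.0247 and p = 0.50 gives 0.0566. Both reproduce.

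**2. Pooling formula.** With N core patients, S supplements selected on the field, core percent correct c, and supplements assumed all present and all correct (the most favourable case):

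- pooled percent correct = (cN + S)/(N + S)
- core value at which the pooled figure reaches 95% = (0.95(N + S) − S)/N
- pooled percent missing = core percent missing × N/(N + S)

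**3. Inputs.** N is about 800 (4.1). Appendix A shows 181 cadaveric recipients already in the cohort. Section 4.3.4 takes about one-third of recipients as having HCV and assumes 100 LDLT and 83 cadaveric recipients with HCV. Section 4.3.1 asks for roughly as many controls as LDLT cases, hence about 100.

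**4. Supplements picked on HCV.** Assume that the one-third share applies to the 181: 181/3 ≈ 60 controls are already present. The shortfall is 83 − 60 = 23 to 100 − 60 = 40.

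**5. Effect across all patients, field 94% correct in the core.**

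| S | Pooled percent correct | Core value that reaches 95% |
|---|---|---|
| 23 | (752 + 23)/823 = 94.2% | (781.85 − 23)/800 = 94.86% |
| 40 | (752 + 40)/840 = 94.3% | (798 − 40)/800 = 94.75% |
| 100 | (752 + 100)/900 = 94.7% | (855 − 100)/800 = 94.4% |
| 200 | (752 + 200)/1000 = 95.2% | (950 − 200)/800 = 93.75% |

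The last two rows use the overall ceiling in 4.1 and require every supplement to have been selected on that one field.

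**6. Effect among HCV patients only.** Assume one-third of 800, about 267, have HCV. A 10% omission rate is 26.7 patients. With 40 supplements it reads 26.7/307 = 8.7%; with 23 it reads 26.7/290 = 9.2%.

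**7. Presence is not correctness.** Let supplements have no missing values but the same error rate as recorded core values, with S = 200. The rates are assumptions, since the protocol gives none.

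- 5% missing, 1% error: core 0.95 × 0.99 = 94.05%; pooled 0.8 × 94.05 + 0.2 × 99 = 95.04%.
- 4% missing, 2% error: core 0.96 × 0.98 = 94.08%; pooled 0.8 × 94.08 + 0.2 × 98 = 94.9%.

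Even at the ceiling, the result depends on how missing values and errors divide.

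**The case against.** A reader might infer that supplements push unreliable fields over the 95% line, for example from 94% to 95.2%. The documents do not support that as an expected result.

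- The line in 4.5.5 is on percent correct, not completeness, and it flags a need for caution rather than acting as a pass/fail gate. No 95% rule is attached to the prospective-cohort aim.
- The example needs 200 supplements, all selected on the same field and all correct. Supplementation is conditional. Against the roughly 250 cadaveric recipients planned, Appendix A already has 181, a gap of 69, and 239 candidates were still waiting. With 69 supplements the same field pools to (752 + 69)/869 = 94.5%.
- Center and transplant date are the only matching fields named. I assume that they are rarely blank in a transplant record. Neither the other matching characteristics nor the validated items are listed, so wider overlap is conjecture.
- The serious omissions noted in 4.5.1 concern HCC, and the HCC comparison uses no supplements.
- Section 4.3.1 allows HCV patients to be identified at the facility if SRTR is incomplete, and patients found that way are not selected on the SRTR field.
- An analysis filter is commonly left to the SAP.

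Most of this stands and limits the size. Three things remain. The facility-level route is optional and depends on SRTR being known to be incomplete, which the validation is meant to establish. Selection on recorded HCV could admit false positives, but 4.3.2 and 4.3.3 require HCV RNA positivity and verification of the diagnosis, so controls who stay in the HCV study should be close to fully correct on that field. Finally, the disagreement among 4.5.1, 4.5.2 and 4.5.3 over who is included lies in the protocol itself.

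**Conclusion.** The point holds as a minor one. If SRTR-selected supplements are pooled, percent missing is understated for any field used to select them, and nothing in 4.5.5 prevents this. For HCV diagnosis, the main exposed field, the expected shift in percent correct over all patients is a few tenths of a point: 94% becomes at most 94.2% to 94.3%, and only a field already at about 94.75% to 94.86% would reach 95%. The distortion is more visible where omissions are counted among HCV patients, with 10% reading about 8.7%.

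These figures rest on four assumptions: a one-third HCV share among the 181 cadaveric recipients and among the 800 core patients, 23 to 40 HCV controls drawn from SRTR, HCV diagnosis being among the validated items, and supplements that are complete and correct on that field. The shift to 95.2% is an upper bound and should not be read as the likely result.

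**What to change.** 1. Reconcile 4.5.1, 4.5.2 and 4.5.3 so that they state one rule on whether supplemental cadaveric cases enter the validation.
2. In 4.5.5, for each SRTR field used to select or match supplements (at least HCV diagnosis), compute percent missing, changed and correct in the cohort evaluated for LDLT only, and show SRTR-selected supplements separately.
3. Keep supplements in the estimates for fields unrelated to their selection. Removing the inclusion sentence from 4.5.1 altogether would discard valid data on those fields.

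The cost is a change of wording and an analysis filter. About 800 patients remain for the affected fields, against the 300 assumed in 4.5.4. Intervals for those fields become slightly wider and their percentages slightly less favourable.

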37 outcomes will be compared with those of transplant candidates who are evaluated for but
38 do not receive LDLT. The primary objective concerns comparison of morbidity and
39 mortality of patients who receive LDLT with a group or groups of patients with similar
40 illnesses and prognoses. It is also important to compare the outcomes after LDLT to
41 those after cadaveric transplantation. Transplant physicians need this information on
42 outcomes to advise patients and prospective donors. Therefore, sufficient patient and
43 donor pairs will be recruited to determine whether recipients of LDLT have substantially
44 different survival than non-LDLT recipients. A large number of donors and recipients

45 from several geographically distributed institutions will be necessary to reliably
46 determine if outcomes are different with the two approaches.

47
48 These issues are best addressed through prospective data collection. But, the main
49 outcomes of the A2ALL prospective data collection will not be available for at least 5
50 years. Therefore, to gain initial insights into outcomes associated with these procedures,
51 a retrospective cohort or look back study has been designed to compare the outcomes of
52 LDLT and cadaveric liver transplants and the outcomes for living liver donors beginning
53 in 1998 at the nine participating transplant centers of the A2ALL study. In order to be
54 conducted rapidly and efficiently, this study will rely exclusively on existing medical
55 records and patient materials.

56 **3. Study Objectives/Specific Aims**

57 **3.1. Overall Aim of the Retrospective Cohort Study**

58 The primary study objective is to determine whether the *decision* to undergo LDLT is
59 beneficial for the patients who choose LDLT. The principal hypothesis is that receipt of
60 a living liver allograft leads to better long term outcomes for liver transplant candidates
61 than *pursuit* of cadaveric transplant. This is a study of the decision to perform LDLT.
62 Several different patient outcomes will be considered.

63 **3.2. Comparison of mortality between LDLT and non-LDLT recipients**

64 **3.2.1. Primary Aim**

65 To compare the survival distribution from time of identification of a potential living
66 donor between those receiving an LDLT and those not receiving one.

67 **3.2.2. Secondary Aims**

68 To compare the survival of LDLT vs. cadaveric recipients from time of transplant.

- 69

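### SRTR validation: the reference value may rest on personal knowledge, and SRTR values the chart cannot confirm count as correct whenever the coordinator keeps them

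*Protocol*

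**What the plan says.** Protocol 4.5.1 first asks the coordinator to provide the "data, based on chart review, for a selected subset of SRTR data items. The coordinator" is then told not to consult the SRTR forms but to work from "chart review (or personal knowledge) alone. These data will be entered in a web-based" module. That module will "check the new data against the original SRTR data and provide immediate feedback if a" discrepancy appears, and the coordinator settles the difference. For storage, the section names the original SRTR record and "the final online entry, will be recorded in a special validation database". It does not list the source of the final value.

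The section gives a reason for letting SRTR values stand. They were submitted nearer to listing and transplant, and may draw on information available at those "times that was not documented in the patient charts. Thus, if a discrepancy is found" the coordinator has the "opportunity to decide which is correct". It also warns that the coordinator may be the person who enters the SRTR/OPTN data, or that person's co-worker. Training is the stated safeguard.

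Section 4.5.5 reports three percentages per data element: (1) missing in SRTR and completed in the new data, (2) present in SRTR and changed, (3) correct in SRTR. They should total 100%, with one named exception: where an "original SRTR data value was deemed to be incorrect and replaced with a missing value". Elements below 95% correct are to be analyzed with caution in the full SRTR database.

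Section 2 describes the retrospective study as a whole: to be "conducted rapidly and efficiently, this study will rely exclusively on existing medical" records and patient materials.

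**The concern.** A validation study needs a reference that is independent of the value being checked. If the coordinator also submitted the SRTR value, personal knowledge is the same source consulted twice, and agreement shows nothing about accuracy.

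The second difficulty is the chart-silent value: present in SRTR, not documented in the chart. The protocol expects such values but gives them no class. If kept, they are pooled with values a record has confirmed. If judged wrong and blanked, they leave the three classes. Percent correct for a poorly charted element then depends partly on how coordinators treat unverifiable entries.

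Three uses depend on the result: the 95% caution rule, the choice of OPTN elements for the prospective cohort, and the feedback to SRTR and OPTN (3.5.2). Because 4.5.1 lists no source field for the validation database, a later analysis plan could not separate confirmed values from unconfirmed ones.

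**Working it through.** **The plan's own figures.** Section 4.5.4 gives 95% confidence interval half-widths for n = 300. With 1.96 × √(p(1−p)/300), p = 0.95 gives 0.0247 and p = 0.50 gives 0.0566. These match the stated 0.025 and 0.057. The point here is classification, and these figures are not in dispute.

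**Where each combination goes under 4.5.5.**

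| SRTR value | Final entry | Class |
|---|---|---|
| Missing | Completed | (1) |
| Present | Changed | (2) |
| Present | Confirmed by chart | (3) |
| Present, chart silent | Kept | (3) |
| Present | Judged wrong, blanked | None |
| Missing | Still missing | None |

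**Denominator.** It is not stated. If it were the sum of the three classes, they would always total 100% and the named exception would have no purpose. The wording therefore implies that blanked values stay in the denominator. On that reading they lower percent correct, but they are not in (2).

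**Possible inflation.** Let p be the true proportion correct (taken as the same in charted and uncharted values) and u the share present in SRTR but not verifiable from the chart. The documents give no value for u, so it is an assumption throughout.

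- All such values kept: reported correct = (1−u)p + u.
- All blanked: reported correct = (1−u)p.
- Share needed to read 95% when all are kept: u = (0.95−p)/(1−p).

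| p | u | All kept | All blanked |
|---|---|---|---|
| 0.94 | 0.20 | 0.752 + 0.20 = 0.952 | 0.752 |
| 0.93 | 0.30 | 0.651 + 0.30 = 0.951 | 0.651 |
| 0.90 | 0.30 | 0.630 + 0.30 = 0.930 | 0.630 |

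The share needed to reach 95% is 0.01/0.06 = 0.167 at p = 0.94 and 0.02/0.07 = 0.286 at p = 0.93.

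**Effect of the keep-or-blank choice near 95%.** Assumed counts: 300 values, 6 missing then completed, 6 changed, U chart-silent, and the remaining 288 − U chart-confirmed.

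| U | Correct, all kept | Correct, all blanked | Three-class total if blanked | Correct among the 300 − U others |
|---|---|---|---|---|
| 6 | 288/300 = 96.0% | 282/300 = 94.0% | 98% | 282/294 = 95.9% |
| 15 | 288/300 = 96.0% | 273/300 = 91.0% | 95% | 273/285 = 95.8% |
| 30 | 288/300 = 96.0% | 258/300 = 86.0% | 90% | 258/270 = 95.6% |

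Six values in 300 are enough for the choice to cross the 95% mark.

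**Understated error class.** With U = 6 all judged wrong and blanked, (2) still reads 6/300 = 2.0%, although 12/300 = 4.0% were judged wrong. The shortfall from 100% does not repair this, because it also holds values missing in both sources. If 9 of the 300 are missing in both, chart-confirmed values fall to 273 and the total is (6 + 6 + 273)/300 = 95.0%. Of that 5-point shortfall, only 2 points are judged errors.

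**The case against.** The best reply is that the text permits inflation without requiring it. Nothing in 4.5.1 says that a chart-silent value is kept, and blanking such values pushes percent correct down. This stands. A reader might infer that poorly charted elements must look the most accurate; the documents support only that they can.

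A reader might also infer that errors which are blanked drop out of the results. The exception to the 100% total speaks against this. Such values still lower percent correct, and moving them into (2) would change no 95% decision. What remains is that (2), the only class that counts errors, omits them.

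Other safeguards exist. Section 4.2.3 says sample records will be examined for completeness before formal collection, which works against large u. Section 4.5.1 trains coordinators to use the chart. Section 7.3 provides source-document requests and at least one site visit, which could detect a sampled value with no source, so it would be too strong to call such values beyond audit. Section 7.4 logs database changes. None of these withdraws the permission to use personal knowledge, records the source of every value, or creates a class for what cannot be verified.

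The Manual of Operations (section 8) is not shown and may define codes. It would still have to work with the three classes fixed in 4.5.5. The conflict with section 2 is mild, since that is a general statement about the design. Finally, SRTR values submitted nearer the event may well be right. That is a reason to report them separately, not to count them as verified.

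**Conclusion.** The point holds in this form. Percent correct in the SRTR substudy mixes chart-confirmed values with unverifiable values that the coordinator chose to keep, and the permitted reference source need not be independent of the SRTR entry. If all such values are kept, the reported figure is (1−u)p + u; if all are blanked, it is (1−u)p. The gap between the two is u itself, so even 2% can decide an element close to 95%. Raising a true 94% or 93% to 95% takes a much larger share, about 17% or 29%. Every size here rests on an assumed u, and the inflation formula also assumes that all unverifiable values are kept. Separately, the error percentage in (2) is understated by whatever is judged wrong and blanked.

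The change should be made, but its reach is limited. The consequence of falling below 95% is caution in analysis, and nothing here bears on the primary survival comparison.

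**What to change.** In 4.5.1, delete the allowance for personal knowledge, or add a field to the validation database giving the source of each final value (chart or other).

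In 4.5.5:
- Add a class for values present in SRTR but not verifiable from the chart, and report its percentage for each element.
- Apply the 95% rule to chart-verifiable values. Beside it, show percent correct with the unverifiable values counted first as all correct and then as all incorrect. The range is needed because leaving them out assumes they are as accurate as the charted ones.
- Count SRTR values judged wrong and set to missing as errors under (2), and state the denominator.

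The cost is one extra entry field, revised class definitions and somewhat wider intervals for poorly documented elements. At p = 0.95 the half-width rises from 0.0247 with 300 values to 1.96 × √(0.0475/270) = 0.0260 with 270, or 0.0295 with 210. The source field has to be in place when data are entered, because it cannot be reconstructed from the two items listed for storage.
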